8.7 Safety analyses

Safety summaries will be conducted on the safety population (treated subjects) and will be performed for all safety variables specified below:

- Adverse events;
- Laboratory tests;
- Vital signs;
- Central Electrocardiograms (ECG);
- Brief neurological assessments;
- Physical Examinations;
- SOWS.

All safety data will be summarized by treatment group.

The safety summaries of changes from baseline to a specific time point in safety variables (e.g., laboratory parameters, vital signs, and ECG) will only include subjects from the safety population who have data available for both the baseline and the time point under consideration unless otherwise specified. No statistical tests will be performed.

8.7.1 Adverse events

All adverse events (AEs) will be classified by SOC and PT according to the MedDRA Version 21.0 or higher.

In summaries by SOC and PT, adverse events will be sorted by decreasing frequency within each SOC and PT according to the total group. In summaries by PT, AEs will be sorted by decreasing frequency according to the total group.

Treatment-emergent adverse events (TEAEs) are defined as AEs that started or worsened in severity on or after the first double-blind dose of study medication.

Double-blind period treatment-emergent adverse events (TEAEs) are defined as AEs that started or worsened in severity on or after the first double-blind dose of study medication and prior to the first extension titration dose of study medication in the open-label period.

Open-label period treatment-emergent adverse events (TEAEs) are defined as AEs that started or worsened in severity on or after the first extension titration dose of the study medication.

All TEAEs will be summarized by period (double-blind period and open-label period) and treatment group, presenting the number and percentage of subjects having at least one TEAE and the number of TEAEs occurring in each SOC and PT. A subject with multiple occurrences of an AE will be counted only once in the corresponding AE category.

The following AE summaries will be performed by period:

- An overall summary of the number and percentage of subjects with the specified AEs, the number of episodes in each TEAE category will be presented;
- Exposure-adjusted AE incidence rate (per 100 subject-years) for TEAEs, regardless of study drug relationship by SOC and PT;
- Number and percentage of subjects with TEAEs, regardless of study drug relationship by SOC and PT;
- Number and percentage of subjects with TEAEs suspected to be drug-related by SOC and PT;
- Number and percentage of subjects with CTC grade 3 or higher TEAEs, regardless of study drug relationship by SOC and PT;
- Number and percentage of subjects with CTC grade 3 or higher TEAEs suspected to be drug-related by SOC and PT;

TEAEs starting after the first dose of study medication with a missing severity will be classified as severe. If a subject reports a TEAE more than once within that System Organ Class (SOC)/ Preferred Term (PT), the AE with the highest severity will be used in the corresponding severity summaries.

Relationship, as indicated by the Investigator, is classified as “Not related”, “Unlikely related”, “Possibly related”, “Probably related” and “Definitely related” (increasing strength of relationship). TEAEs with a

missing relationship to study medication will be regarded as “Probably related” to study medication. If a subject reports the same AE more than once within that SOC/PT, the AE with the strongest relationship to study medication will be used in the corresponding relationship summaries. Relationship will be summarized as “Related” and “Unrelated”. Adverse events with investigator indicated drug-event relationship of “Not related” and “Unlikely related” are classified as “Unrelated” with the study medication, while adverse events with drug-event relationship documented as “Possibly related”, “Probably Related” and “Definitely related” are considered as “Related” with the study Medication.

Deaths, Serious and Other Significant Adverse Events

TEAEs leading to Death are those events with an “Outcome” recorded as “Fatal” on the Adverse Events page of the eCRF. The number of subjects with TEAEs leading to death will be summarized by SOC and PT. A listing of all TEAEs leading to death will be provided.

Serious adverse events (SAEs) are those events with a response of “Yes” for the item “Was AE Serious” on the AE eCRF form. Summaries of incidence rates (frequencies and percentages) of SAEs by SOC and PT will be prepared. A by-subject data listing of all SAEs will be provided.

Actions taken with study drug are dose discontinuation and interruption from the eCRF page of Adverse Events. TEAEs leading to drug adjustment will be summarized by SOC and PT for study treatment discontinuation and interruptions.

The following summaries of TEAEs will be provided:

- TEAEs leading to deaths, by SOC and PT;
- Serious TEAEs, regardless of study drug relationship, by SOC and PT;
- Serious TEAEs suspected to be drug-related, by SOC and PT;
- TEAEs leading to drug interruption by SOC and PT;
- TEAEs leading to study drug discontinuation by SOC and PT.

Listings to be provided are:

- AEs leading to Deaths (CRF Adverse Event page: AE outcome is Fatal.);
- Serious AEs;
- AEs leading to dose interruption and discontinuation, respectively;
- All deaths with date of event, study day, AEs reported around the time of death etc.

8.7.2 Clinical laboratory evaluations

All laboratory data will be summarized in the International System of Units (SI) and conventional units, respectively. Quantitative laboratory measurements reported as “< X”, i.e. below the lower limit of quantification (BLQ), or “> X”, i.e. above the upper limit of quantification (ULQ), will be converted to X for the purpose of quantitative summaries, but will be presented as recorded, i.e. as “< X” or “> X” in the listings. All laboratory assessments will be listed.

Descriptive statistics of absolute value and change from baseline (mean, SD, median, minimum, and maximum) for continuous assessments will be presented by windowed visits.

Laboratory Reference Ranges High/Low Criteria and Investigator's Assessment

Quantitative laboratory measurements will be compared with the relevant laboratory reference ranges in SI units and categorized as:

- Low: Below the lower limit of the laboratory reference range;
- Normal: Within the laboratory reference range (upper and lower limit included);
- High: Above the upper limit of the laboratory reference range.

Shift tables (Low, Normal, High) from baseline to worst post-baseline in lab parameters for each treatment group in the double-blind treatment period will be displayed.

Values outside the normal range will be flagged in the listings of individual subject data. Unscheduled visits will not be included in the analysis but will be listed.

Hepatobiliary Laboratory Abnormalities

Treatment emergent hepatobiliary laboratory abnormalities defined as values outside pre-specified thresholds will be summarized and listed by treatment and windowed visit. Treatment emergent is defined as any disorder/event recorded on the eCRF which started on or after the start date of treatment.

A summary of any treatment emergent hepatobiliary laboratory abnormalities according to different pre-specified thresholds will be made by treatment group:

- ALT or/and AST >3 x ULN and ≤ 5 x ULN;
- ALT or/and AST >5 x ULN;
- Total bilirubin >2 x ULN;
- (ALT and/or AST >3 x ULN) and Bilirubin > 2 x ULN;

- Hy's law laboratory criteria: (ALT and/or AST $>3 \times$ ULN) and Bilirubin $> 2 \times$ ULN and ALP $<2 \times$ ULN.

ULN = Upper limit of normal range.

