Additional tests and other evaluations required to establish the significance or etiology of an abnormal result or to monitor the course of an AE will be obtained when clinically indicated. In particular, if a clinically significant abnormal result is observed that is not resolved by the final study visit, tests will be repeated to document resolution or stability of the abnormality.

Specifically defined reflex testing, which will be performed for abnormal results, include:

- On-study TSH values above or below the upper or lower limit of normal (ULN or LLN), will result in reflex testing for Free T4 from the existing laboratory sample (when sample is insufficient, a re-draw is necessary).
- A positive HCV antibody will have HCV RNA processed from the existing laboratory sample, if possible (or on a re-draw if the original sample has insufficient material). The subject may not be enrolled if the HCV RNA result is detectable. Referral to a hepatologist or infectious disease specialist is recommended for consideration of antiviral treatment. Subject may be reconsidered, as appropriate, after treatment.

Table-4. Clinical Laboratory Assessments		
Serum Chemistry/Serology/Other	Hematology	Urine

 • Alanine aminotransferase • Albumin • Alkaline phosphatase • Aspartate aminotransferase • Bicarbonate • Blood urea nitrogen • Calcium (screening) • Chloride • Creatinine • Direct bilirubin • Estimated glomerular filtration rate • Gamma-glutamyl transferase • Glucose (random) • Indirect bilirubin • Lactate dehydrogenase • Potassium • Phosphate • Pregnancy • Sex hormone binding globulin (for biological males) • Sodium • Free testosterone (for biological males only) • Thyroid stimulating hormone (with reflex Free T4 if > ULN or < LLN) • Total bilirubin • Total protein • Uric acid • HCV antibody (if positive, then reflex HCV RNA; at screening only) • IgA-TTG (at screening only) 	
 • Hematocrit • Hemoglobin • Platelet count • Red blood cell count • White blood cell count • White blood cell differential 	
 • Urinalysis • Pregnancy

HCV = hepatitis C virus; IgA-TTG = Immunoglobulin A tissue transglutaminase.

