7.2.7. Visit Window Definitions

Windowing is applicable to efficacy and safety endpoints, except for WI-NRS and SOWS for reporting purposes.

	BL*	Week 2	Week 6	Week 10	Week 14 **	Week 16	Week 20	Week 24	Week 28	Week 32	Week 36	Week 44	Week 52	Week 54	Week 56
Scheduled Day	1	14	42	70	98	112	140	168	196	224	252	308	364	378	
ItchyQoL	Day 1		22 to 56	57 to 84	85 to (titration start day-1)		titration start day to 154	155 to 182	183 to 224		225 to 280	281 to 336	>=337		
PAS and IGA-PN	Day 1			29 to 84	85 to (titration start day-1)		titration start day to 154	155 to 182	183 to 210	211 to 238	239 to 280	281 to 336	>=337		
PBI-P	Day 1			29 to 84	85 to (titration start day-1)		titration start day to 168		169 to 210	211 to 238	239 to 280	281 to 336	>=337		
Sleep Scale	Day 1		22 to 56	57 to 84	85 to (titration start day-1)		titration start day to 154	155 to 182	183 to 224		225 to 280	281 to 336	>=337		
Vital Signs	Day 1	8 to 28	29 to 56	57 to 84	85 to (titration start day-1)	titration start day to 126	127 to 154	155 to 182	183 to 210	211 to 238	239 to 280	281 to 336	337 to 371	>=372	
Clinical lab	Day 1	8 to 28	29 to 70		71 to (titration start day-1)				106 to 252			253 to 336	337 to 371	>=372	
Urinalysis	Day 1								99 to 280				>=281		

* If a Day 1 value is missing, then the last screening value is used as the baseline value.

** In the Week 14 column, the end of the window applies to subjects who go on to enter the open-label period. For subjects who don't enter the open-label period, the end of the window is 14 days later than that displayed in the column.

Statistical Analysis Plan (SAP)

Note: ECG windowing will be established by ERT, who will perform ECG analyses.

If two or more observations fall into the same window, the observation closest to the scheduled day will be used in the analysis. If there is a tie, the later observation will be used.

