8. STATISTICAL METHODS AND ANALYSIS

8.1 General Statistical Conventions

All statistical procedures will be completed using SAS 9.4® or higher.

Unless otherwise stated, all statistical testing will be two-sided and will be performed using a significance (alpha) level of 0.05, and two-sided 95% confidence intervals (CI) will be provided when relevant.

Continuous variables will be summarized using descriptive statistics, including number of subjects (n), mean, median, standard deviation (SD), minimum and maximum. For efficacy variables with subscales, the total score and subscales will be summarized.

For categorical variables, summaries will include counts of subjects and percentages. Percentages will be rounded to one decimal place.

Unless otherwise stated all summaries will be presented by treatment group.

All subject data, including those derived, will be presented in individual subject data listings. Unless otherwise stated, unscheduled visit results will be included in date/time chronological order, within subject listings only. All listings will be sorted by treatment group, subject ID, date/time and visit/study day. Subject's sex and age will be stated on each listing. Unless otherwise stated, data listings will be based on All Subjects Randomized Set.

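### The laboratory shift tables to worst post-baseline leave out unscheduled draws, and the liver threshold counts appear to do so too

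*SAP*

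**What the plan says.** For the double-blind period, SAP 8.7.2 states: "Shift tables (Low, Normal, High) from baseline to worst post-baseline in lab parameters for each treatment group in the double-blind treatment period will be displayed". Under the same reference-range subheading it adds: "Unscheduled visits will not be included in the analysis but will be listed". SAP 8.1 sets the default for the whole plan: "Unless otherwise stated, unscheduled visit results will be included in date/time chronological order, within subject listings only".

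The hepatobiliary subheading comes next and describes two outputs. The first: "Treatment emergent hepatobiliary laboratory abnormalities defined as values outside pre-specified thresholds will be summarized and listed by treatment and windowed visit". The second is a summary, by treatment group, of any treatment-emergent abnormality against a list of thresholds that ends with the Hy's law criteria. It names no visit or window.

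Four other places bear on this:
- SAP 7.2.7, on windows: "If two or more observations fall into the same window, the observation closest to the scheduled day will be used in the analysis".
- SAP 7.2.1 lets repeat and unscheduled assessments supply the baseline value.
- Protocol 12.3: extra tests needed to explain an abnormal result or "to monitor the course of an AE will be obtained when clinically indicated".
- Protocol 13.4.7.3 bases laboratory summaries on the first measurement of each scheduled assessment, omits same-time-point repeats from the calculations, and lists every value.

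**The concern.** A worst-value table or a threshold count asks whether a subject ever reached a given level after starting treatment. Extra draws are ordered because a result was abnormal or an adverse event needed follow-up, so they are more likely than routine draws to hold the extreme value. Leaving them out suits a mean at Week 6, but it changes the answer to the ever-reached question.

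The two ends of the shift also follow different rules: an unscheduled value can set the baseline but cannot be the worst value afterwards.

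At stake is the only arm-level comparison of laboratory abnormalities. Protocol 12.1.2 records a laboratory abnormality as an adverse event only if it comes with clinical symptoms or events and worsens after treatment starts. A symptom-free ALT rise found at an extra draw can therefore be absent from the adverse event tables and the shift table, and possibly from the liver threshold table. It would then appear only in a subject listing.

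**Working it through.** The plan gives no figure to reproduce. The check applies its rules to cases.

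**Inputs from the documents.** Scheduled double-blind laboratory draws after baseline are at Weeks 2, 6 and 14 (Days 14, 42 and 98; Protocol Table 1). The laboratory windows in SAP 7.2.7 are Days 8 to 28 for Week 2, Days 29 to 70 for Week 6, and Day 71 to the day before extension titration for Week 14. The liver thresholds are those in SAP 8.7.2.

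**Case A, shift table (invented values).** ULN 40; ALT 30, 38 and 36 at Days 14, 42 and 98; unscheduled ALT 220 at Day 60 and 130 at Day 67.
- Scheduled values only: worst = 38/40 = 0.95 x ULN, tabulated Normal.
- All values: worst = 220/40 = 5.5 x ULN, tabulated High and in the >5 x ULN row.

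**Case B, liver thresholds (invented values).** ALT 2.8 x ULN at Day 42, 6 x ULN at an unscheduled draw on Day 49, normal at the other scheduled draws.
- Both values fall in the Week 6 window. Distances from the scheduled day are |42 - 42| = 0 and |49 - 42| = 7, so the Day 42 value is kept.
- Kept maximum = 2.8 x ULN: neither the >3 to 5 x ULN row nor the >5 x ULN row.
- All values: maximum = 6 x ULN, in the >5 x ULN row.

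The nearest-day rule alone produces this result in any output built on windowed values, even if unscheduled draws were admitted to the windows. In Case B the shift table is not affected, because 2.8 x ULN is already High. That table changes only when every scheduled value is normal, or abnormal in the other direction.

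**How often could an episode fall between scheduled draws?** This is an illustration under assumptions that are not in the documents: onset is uniform over Days 1 to 98 and the episode lasts D consecutive days. For each onset day o, the episode is missed by the schedule if none of Days 14, 42 and 98 lies in o to o + D - 1. Share missed = missed onset days / 98.

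| D (days) | Missed onset days | Share |
|---|---|---|
| 7 | 77 | 79% |
| 14 | 56 | 57% |
| 21 | 42 | 43% |
| 28 | 28 | 29% |
| 42 | 14 | 14% |

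These shares describe episodes that only an extra draw could detect. They are not the share detected at an extra draw and then left out of the tables, which would need the frequency of unscheduled draws. The documents do not give that frequency.

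**The case against.** The strongest reply has five parts.

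1. **Reach of the sentence.** The exclusion stands under the reference-range subheading, before the hepatobiliary one. A reader might infer that it expressly removes unscheduled draws from every liver count. It does not. The reach comes from the SAP 8.1 default, the windowed-visit wording and SAP 7.2.7. The by-treatment-group summary covers any treatment-emergent abnormality, and SAP 8.7.2 defines treatment-emergent by onset on or after the start of treatment, without reference to a window. Whether that overrides the default is open. This part stands: for that summary the plan is unclear, and the omission is not certain.

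2. **Values are not hidden.** All laboratory results are listed and out-of-range values flagged (SAP 8.7.2). Protocol 13.4.7.3 adds a listing of markedly abnormal values, and a DSMB reviews group-level safety data (Protocol 12.2). A reader might infer that liver signals will go unseen; the documents do not support that. Listings, however, give no count by arm.

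3. **More draws than three.** Subjects who stop drug have laboratory tests at the Off-Treatment visit and again at the Last Visit (Protocol 9.1.3.6). These may catch some episodes in the group where marked elevations might be expected. This stands as a limit on the size of the problem.

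4. **Repeats are not all unscheduled.** A raised TSH is repeated at the next study visit or about a month later, whichever comes first (Protocol Table 1, footnote 5), and reflex tests use the existing sample where possible (Protocol 12.3). This also stands.

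5. **The SAP largely follows the protocol.** Protocol 13.4.7.3 is not confined to by-visit summaries, so the change departs from protocol text and must be recorded as such. That affects the paperwork. It does not make the worst scheduled value the worst value.

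**Conclusion.** The point holds for the shift tables on the stated text: SAP 8.7.2 promises the worst post-baseline value and then excludes the draws ordered to follow up abnormal results. For the liver and Hy's law thresholds, the plan's default and window rules would drop a peak seen at an unscheduled draw from the by-visit summary. They leave the by-treatment-group summary ambiguous.

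The effect is confined to summary counts between arms. No number of affected subjects can be derived, because it depends on how many unscheduled draws were taken and what they showed. If the drug causes more abnormalities, more of the omitted values would come from the active arm, but the documents do not establish that. Efficacy and type I error are untouched. The plan should be changed because a table's label and its content disagree and the data to correct it are already collected.

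**What to change.** In SAP 8.7.2, state that the worst post-baseline shifts and all hepatobiliary threshold counts by treatment group, including Hy's law, use every value after the first dose within the relevant period, whether scheduled, unscheduled or repeat, regardless of visit window. The last condition also brings in Days 2 to 7, which fall in no laboratory window because the first one opens at Day 8. Keep the present exclusion for by-visit descriptive statistics. Say in the same place how worst is chosen for tests that can be abnormal in both directions.

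Record the change in SAP section 9 as a departure from Protocol 13.4.7.3. The cost is a programming filter and a few sentences, with no new data. Abnormality counts may rise slightly.

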13.4 Statistical Methods

13.4.1 General Principles

Summary statistics will be presented by treatment group. For continuous variables, unless otherwise stated, the number of available observations (n), mean, standard deviation, median, and range will be provided. For categorical variables, the number and percentage in each category will be displayed.

For the open-label extension period, summary statistics will be presented by treatment group (as per the double-blind period) and overall as a single group. Only descriptive statistics will be displayed for open-label extension period.

Assessments of change from baseline to post-baseline will include only those subjects with both baseline and post-baseline measurements. Baseline for WI-NRS is derived as the average of the responses on the 7 days prior to the first dose of investigational product. For other variables, the last value of a variable taken before the first dose of investigational product will be used as the baseline value.

A more detailed description of study analyses will be presented in the SAP.

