- To evaluate the effect of NAL ER on itch-related quality of life as assessed by the ItchyQoL total score.
- To evaluate the effect of NAL ER on Prurigo Nodularis (PN) skin lesions as assessed by the Prurigo Activity Score (PAS) Question 5a.
- To evaluate the effect of NAL ER on sleep as assessed by the PROMIS Sleep Disturbance Short Form 8a.

Other secondary objectives:

- To evaluate the effect of NAL ER on itch as assessed by the mean change in WI-NRS.
- To evaluate the benefit to subjects of NAL ER using the Patient Benefit Index, pruritus version (PBI-P).
- To evaluate the safety and tolerability of NAL ER.
- To assess the PK of nalbuphine and its metabolites.

III. STUDY DESIGN

A. General study design

This is a randomized, double-blind, placebo-controlled, 2-arm study, with an open-label extension period following double-blind treatment, to investigate NAL ER tablets' anti-pruritic efficacy and

safety. Subjects will be randomized to NAL ER (2-week titration followed by 162-mg BID for 12 weeks) or matching placebo (14 weeks duration), with the primary endpoint evaluation at Week 14. If permanent discontinuation of investigational product occurs anytime between Day 1 and the Week 14 visit, the subject must complete the off-treatment visit and procedures, and must return to the clinic for ALL remaining study evaluation visits up to and including the Week 14 visit. During the open-label extension, subjects who received NAL ER will continue on NAL ER for a total of 38 additional weeks (total treatment duration 52 weeks including titration) and subjects who received placebo will crossover to NAL ER for a total of 38 weeks (including titration). Upon discontinuation of investigational product, all subjects will complete a 2-week off-treatment safety follow-up period, regardless of when and why the subject discontinued study treatment unless they withdraw consent. In addition, a final follow-up itch and safety assessment will be made via phone call 4 weeks after the last dose of investigational product. The total planned study duration from randomization through the last phone contact is 56 weeks.

Approximately 240 subjects with diagnosed PN will be randomized (1:1) to one of the following treatment arms:

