7.2.3. Date of First Dose of Study Drug

The date of randomization will be utilized for the date of first study drug dose, and will be referred to as the start date of study drug.

For the analysis referring to the open-label period, the date of the first administration of the extension titration medication will be considered as the start of this period.

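### The liver threshold summary in SAP 8.7.2 has no end at crossover and no period split, so read literally it counts abnormalities first arising on NAL ER in the placebo column

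*SAP*

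**What the plan says.** The hepatobiliary part of SAP 8.7.2 contains three statements that matter here.

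- The window: "Treatment emergent is defined as any disorder/event recorded on the eCRF which started on or after the start date of treatment". SAP 7.2.3 fixes the start: "The date of randomization will be utilized for the date of first study drug dose". No end date is given.
- A display by visit: the abnormalities "will be summarized and listed by treatment and windowed visit".
- A threshold summary: "A summary of any treatment emergent hepatobiliary laboratory abnormalities according to different pre-specified thresholds will be made by treatment group". The thresholds are bands of ALT or AST, total bilirubin above twice the upper limit of normal, the combination of the two, and the Hy's law criteria. No period is named.

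Other rules in the plan do set a limit. SAP 8.7.1 defines double-blind treatment-emergent adverse events as those starting or worsening "on or after the first double-blind dose of study medication and prior to the first extension titration dose of study medication in the open-label period", and reports adverse events by period. Within SAP 8.7.2, the laboratory shift tables to the worst post-baseline value cover only the double-blind period.

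Placebo subjects who continue move to NAL ER after Week 14 for 38 weeks (SAP, General study design). On extension data, protocol 13.4.1 says: "For the open-label extension period, summary statistics will be presented by treatment group (as per the double-blind period) and overall as a single group".

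**The concern.** A placebo-arm subject whose first ALT above 3 times the upper limit of normal is drawn at Week 28 has been on NAL ER since Week 15. That value meets the treatment-emergent definition, and the treatment group is still the randomised one. A programmer following SAP 8.7.2 as written would therefore add the subject to the placebo count.

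In a completed study, the NAL ER column would then hold up to 52 weeks of NAL ER. The placebo column would hold 14 weeks of placebo plus up to 38 weeks of NAL ER. Compared side by side, the columns would understate a hepatic effect if there is one. The denominators would be wrong as well: every treated subject in the arm would be in them, although only those who enter the extension can have an open-label abnormality.

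The final report is not the only place this arises. SAP 8.8 puts the primary analysis at the point when the last subject finishes double-blind treatment, and by then earlier enrollees will already have open-label laboratory data.

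**Working it through.** The plan states no figure for this summary, so there is nothing to reproduce. The check compares the counting rules and then works out how much of the placebo column is NAL ER exposure.

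**Rules side by side**

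| Output | Window | Split at crossover? |
|---|---|---|
| Adverse events (SAP 8.7.1) | Double-blind window closes at the first extension titration dose | Yes |
| Laboratory shift tables (SAP 8.7.2) | Double-blind period only | Yes |
| Liver display by visit (SAP 8.7.2) | Open-ended, in visit windows; Week 14 closes the day before extension titration (SAP 7.2.7) | Yes, by row |
| Liver threshold summary (SAP 8.7.2) | Open-ended from the start of treatment | No |

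**Exposure, from the study design.** Placebo lasts 14 weeks and NAL ER after crossover lasts 38 weeks. For a completer, the NAL ER share of the placebo column is 38 / (14 + 38) = 38/52 = 73%.

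**Scheduled draws, from the protocol schedules of assessments.** Post-baseline chemistry falls at Weeks 2, 6 and 14 before crossover and at Weeks 28, 44 and 52 after it. That makes 3 of 6 draws on NAL ER. Counting the Week 54 off-treatment visit, 4 of 7 laboratory windows fall after crossover.

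**Illustration of the attenuation.** The documents give no liver event rate and no extension retention, so both are assumed. Let R be the true NAL ER to placebo rate ratio, constant over time.

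- By time, all subjects completing: apparent ratio = 52R / (14 + 38R).
  - R = 2: 104/90 = 1.16
  - R = 3: 156/128 = 1.22
  - R = 5: 260/204 = 1.27
  - The ratio cannot exceed 52/38 = 1.37.
- By scheduled draws through Week 52: apparent ratio = 6R / (3 + 3R). For R = 3: 18/12 = 1.50.
- By time, with 70% entering and completing the extension in each arm: open-label weeks average 0.7 × 38 = 26.6, and total weeks average 14 + 26.6 = 40.6. The NAL ER share is 26.6/40.6 = 66%. For R = 3: (40.6 × 3) / (14 + 26.6 × 3) = 121.8/93.8 = 1.30.

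**Check on subject-level risk.** This uses an assumed 14-week placebo risk b of 0.5% to 2%, with weekly hazard h = −ln(1 − b)/14. With full retention, the placebo column risk is 1 − exp(−h(14 + 38R)) and the NAL ER column risk is 1 − exp(−52hR). For b = 1% and R = 3 these are 0.088 and 0.106, a ratio of 1.21. Over b = 0.5% to 2%, R = 2 to 5 and 60% to 100% retention, the open-ended ratio runs from 1.14 to 1.43. A window closed at crossover gives 1.98 to 4.95 for the same inputs. In the open-ended table, 75% to 93% of subjects counted under placebo would have their first abnormality only after crossover.

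**The case against.** The strongest reply is that the sentence is silent on period and the general rules fill the gap. Protocol 13.4.1 opens with the words for the open-label extension period, and an overall single-group column makes sense there because everyone is then on NAL ER. SAP 7.2.3 gives the open-label period its own start date. Both point toward separate open-label presentation. The threshold sentence could also be read as listing the cut-offs for the visit display rather than ordering a second table. The table templates are in a separate document (SAP, Introduction) and may split by period.

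Much of this stands. The general rules show a likely intention, and the templates cannot be checked. However, SAP 8.7.2 does not invoke those rules. It writes its own emergent definition, with a start and no end, and the second sentence drops the visit dimension that the first one has. The safety-population rule on treatment actually received does not help either: SAP 6.2 and 8.2 apply it to misallocation, not to planned crossover.

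A reader might infer more than the documents support:

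- That a Hy's law case on NAL ER would be hidden under placebo. The visit display, whose Week 14 window ends before extension titration, and the listing of all laboratory values would both show such a case at its true time. An abnormality reported as an adverse event is split by period.
- That this is the table on which a liver signal will be judged. No section gives it that role. Protocol 13.4.7 and SAP 8.7 keep safety descriptive, without tests.
- That the ratios above are an expected effect. They depend on hazards and retention that the documents do not give.

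**Conclusion.** The point holds for the summary of any abnormality by threshold and for its denominators, and no further. As written, SAP 8.7.2 would place abnormalities first arising on NAL ER after crossover in the placebo column, although the plan's adverse event rule and its shift tables avoid this.

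The 73% of treatment weeks and the 3 of 6 draws follow from the schedule for a subject who completes the study. They will be lower at the primary analysis, when extension follow-up is partial, and lower with dropout. The apparent ratio of about 1.2 to 1.5 for a true ratio of 3 is an illustration. It assumes a constant hazard, and the lower and upper ends also assume full retention and counting by time or by draws respectively. A hazard that changes with time on drug would give other values.

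No test or decision rule depends on this table, and individual cases remain traceable. The correction is worth making because the summary would mislead anyone who read it as a placebo comparison.

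**What to change.** In SAP 8.7.2, apply the period rule of 8.7.1 to the threshold summary.

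1. Double-blind table: post-baseline values before the first extension titration dose, by treatment group. This is the placebo comparison.
2. Open-label table: values on or after that dose, by prior arm (NAL ER continued; placebo to NAL ER) and overall, with subjects who entered the extension as denominators.
3. Any whole-study summary should be labelled as such and not used as a placebo comparison.

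The table templates should carry the same split. The cost is one SAP edit and a period flag that the adverse event tables already need; no new data are required. The downside is one extra table and fewer events in the placebo-controlled one.
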